6. STATISTICAL METHODS

6.1. General Methodology

All statistical tests, summary tables and data listings will be prepared using SAS version 9.3 or higher.

All statistical tests of efficacy parameters will be 2-sided with a significance level of α =0.05, unless specified otherwise. Statistical tests will be supported by presenting estimates and 95% confidence intervals (CI) for each treatment group.

Continuous data will be summarized using descriptive statistics (number of subjects [n], mean, SD, median, minimum, and maximum). Discrete data will be summarized using frequency counts and percentages. The denominator will be based on the number of subjects in the appropriate population.

For the purpose of display, the summary results will be rounded as follows:

- Minimum and maximum: Same number of decimal places as the raw data.
- Mean and Median: One more decimal place than the raw data.

- SD: Two more decimal places than the raw data.
- Percentages will be displayed with 1 decimal place precision. A zero count will be left blank.
- The standard form of a percentage change variable is 0 decimal places.

For categorical variables with missing values, a category documenting the frequency of missing values will be displayed in the summary tables.

Summary tables, subject listings, graphs and any supportive SAS output will include footnotes that will indicate:

- Date of data extraction.
- Date and time of output generation.
- SAS program name, including the path that generated the output.

When calculating percentages, the denominator will be based on the number of subjects with non-missing values. If the denominator is expected to change over time, then the denominator used to calculate the percentage will be based on the number of subjects with non-missing values at each visit. Any subject removed from an analysis will be noted at the bottom of the table along with the reason the subject was removed.

Empty summary tables will be presented with a note stating that "No Subjects Met Criteria."

Subject listings of all data from the eCRFs as well as any derived variables will be presented.

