3. OBJECTIVES AND ENDPOINTS

3.1. Objectives and Endpoints

Objectives		Endpoints
Pri	imary	
•	To assess the efficacy of EN3835 for the treatment of AC of the shoulder using the adapted American Shoulder and Elbow Surgeons Standardized Shoulder Form (ASES) composite score.	• The change from baseline in the adapted ASES composite score for the affected shoulder at the Day 95 Visit.
See	condary	
•	To assess the efficacy of EN3835 for the treatment of AC of the shoulder using passive range of motion (PROM).	• The absolute and percent change from baseline in PROM for forward flexion, internal rotation, external rotation, abduction, and shoulder extension in the affected shoulder at the Day 22, 43, 64, and 95 Visits compared to the contralateral shoulder at baseline.
•	To assess the efficacy of EN3835 for the treatment of AC of the shoulder using active range of motion (AROM).	• The absolute and percent change from baseline in AROM for forward flexion, internal rotation, external rotation, abduction, and shoulder extension in the affected shoulder at the Day 22, 43, 64, and 95 Visits compared to the contralateral shoulder at baseline.
•	To assess the efficacy of EN3835 for treatment of AC of the shoulder using the adapted ASES.	• The change from baseline in the adapted ASES composite score, the adapted ASES function subscale, and the adapted ASES pain subscale for the affected shoulder at the Day 22, 43, 64, and 95 Visits.
•	To assess the impact of EN3835 on pain upon movement (PUM) in subjects with AC of the shoulder.	• The change from baseline in the PUM Scale for the affected shoulder at the Day 64 and Day 95 Visits.
•	To assess the impact of EN3835 on the severity of AC in subjects with AC of the shoulder.	 The change from baseline in the Patient-reported Global Severity of Adhesive Capsulitis Scale at the Day 22, 43, 64 and 95 Visits. The rating (response) in the Patient-reported Change in Severity of Adhesive Capsulitis Scale at the Day 22, 43, 64, and 95 Visits.
•	To assess subject satisfaction with treatment and investigator assessment of improvement with treatment of EN3835 for AC of the shoulder.	 Investigator assessment of improvement with treatment at the Day 64 and Day 95 Visits. Subject satisfaction with treatment at the Day 64 and Day 95 Visits.

Objectives	Endpoints

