9. STATISTICAL CONSIDERATIONS AND METHODS

9.1. Sample Size Determination

A post hoc analysis was conducted using a subgroup of AUX-CC-871 subjects who were rated with moderate/severe AC based on baseline MRI images. This subgroup displayed a notable treatment effect (EN3835 vs placebo) on the pain and composite components of the adapted ASES questionnaire. This subgroup also displayed a treatment effect trend for the functional component of the adapted ASES. Given this result, the sample size calculation is based on the mean and SD found in this subgroup for the adapted ASES composite score on Day 95. Given a mean change from baseline value of 38.6 for the EN3835 group and 27.6 for the placebo group with an SD of 21.6, a sample size of approximately 142 subjects would be required given a 1:1 randomization and a type I error of 0.05 with a power of 85%. With an expected drop-out rate of approximately 20%, 180 subjects (90 EN3835 and 90 placebo) should be dosed to ensure 142 subjects complete the study.

9.2. **Populations for Analysis**

For the purposes of analysis, the following populations are defined:

- The Safety Population is defined as all randomized subjects who received at least 1 injection of study treatment (EN3835 or placebo). All safety analyses will be based on this population.
- The Intent-to-Treat (ITT) Population is defined as all randomized subjects who received at least 1 injection of study treatment (EN3835 or placebo).
- The Modified Intent-to-Treat (mITT) Population is defined as all ITT subjects who have a valid baseline adapted ASES composite score in the affected shoulder and at least 1 valid adapted ASES composite score after the injection of the study treatment. All efficacy analyses will be based on this population.
- The Per-Protocol (PP) Population is defined as those subjects in the mITT Population who do not have any major protocol deviations. Determination of PP subjects will be completed before the study database is closed and locked. If more than 10% of the mITT Population is excluded from the PP Population, then all efficacy summaries will be repeated using the PP Population for the sensitivity analysis.

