7.9.1. Primary Analysis

7.9.1.1. Change from Baseline in Adapted ASES Composite Score

The primary endpoint is the change from baseline to the Day 95 Visit in the adapted ASES composite score.

MMRM will be performed to estimate change from baseline treatment effect at Day 64 and Day 95 Visits comparing active to placebo for the adapted ASES composite score in the affected shoulder. MMRM will be performed to estimate the least square (LS) means of change from baseline for EN3835 and placebo treatment. *P* values and 95% CIs for the treatment difference (EN3835 – Placebo) will be calculated by MMRM for the visits with treatment, visit, and an interaction of treatment and visit as fixed effected and repeated with visit/subject. Autoregressive covariance structure will be used in the model.

Observed values and change from baseline in the adapted ASES composite score in the affected shoulder for each treatment group will be summarized at Day 22, 43, 64 and 95 Visits using descriptive statistics.

A listing of adapted ASES scores will be provided.

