7.9.2. Secondary Analysis

7.9.2.1. Absolute and Percent Change from Baseline in PROM

MMRM will be performed to estimate change from baseline treatment effect at Day 22, 43, 64 and Day 95 Visits comparing active to placebo for PROM for forward flexion, internal rotation, external rotation, abduction, and shoulder extension in the affected shoulder. MMRM will be performed to estimate the LS means of absolute change from baseline for EN3835 and placebo treatment. *P* values and 95% CIs for the treatment difference (EN3835 – Placebo) will be

25-April-2022

calculated by MMRM for the visits with treatment, visit, and an interaction of treatment and visit as fixed effected and repeated with visit/subject. Autoregressive covariance structure will be used in the model.

MMRM will be performed to estimate absolute and percent change from baseline treatment effect compared to baseline of the contralateral shoulder at Day 22, 43, 64 and Day 95 Visits comparing active to placebo for PROM for forward flexion, internal rotation, external rotation, abduction, and shoulder extension in the affected shoulder. MMRM will be performed to estimate the LS means of absolute and percent change from baseline for EN3835 and placebo treatment. *P* values and 95% CIs for the treatment difference (EN3835 – Placebo) will be calculated by MMRM for the visits with treatment, visit, and an interaction of treatment and visit as fixed effected and repeated with visit/subject. Autoregressive covariance structure will be used in the model.

Observed values and change from baseline in PROM for forward flexion, internal rotation, external rotation, abduction, and shoulder extension in the affected shoulder for each treatment group at Day 22, 43, 64, and 95 Visits compared to the affected shoulder at baseline will be summarized using descriptive statistics.

Observed values, absolute and percent change from baseline in PROM for forward flexion, internal rotation, external rotation, abduction, and shoulder extension in affected shoulder for each treatment group at Day 22, 43, 64, and 95 Visits compared to the contralateral shoulder at baseline will be summarized using descriptive statistics.

A listing of PROM will be provided.

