7.9.2.8. Subject Satisfaction with Treatment

A Wilcoxon rank sum nonparametric test will be used to compare EN3835 to placebo for all the individual questions of Subject Satisfaction prior to receiving treatment and Subject Satisfaction compared to better shoulder for the affected shoulder at the Day 64 and 95 Visits. The null and alternative hypotheses for this test will be as below:

H₀: There is no difference in the Subject Satisfaction with Treatment in the 2 treatment groups.

Vs

H₁: Subject Satisfaction with Treatment differs in the 2 treatment groups.

Wilcoxon scores (Rank Sums) for treatment group and test statistics along with p value for the test of significance will be presented.

Reponses for Subject Satisfaction with Treatment in the affected shoulder and responders will be summarized by treatment group using frequency counts and percentages with mean and SD.

A listing of Subject Satisfaction with Treatment scores will be provided.

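### SAP 6.1 sets every efficacy test at two-sided 0.05, and 113 distinct secondary contrasts are tested with no hierarchy, no gate on the primary and no nominal label

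*SAP*

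**What the plan says.** The primary endpoint is one contrast: EN3835 against placebo for change from baseline in the adapted ASES composite at Day 95 (Protocol 3.1 and 9.3.1; SAP 2, 6.3.1 and 7.9.1.1).

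SAP 6.1 gives one rule for all efficacy tests: "All statistical tests of efficacy parameters will be 2-sided with a significance level of α =0.05, unless specified otherwise". No later section sets a different rule for any secondary test. Protocol 9.3.1 has no multiplicity rule, and the list of changes in SAP 8 adds none.

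The secondary tests are numerous and are written as inference:

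- The primary-analysis section also produces a Day 64 comparison of the composite: "MMRM will be performed to estimate change from baseline treatment effect at Day 64 and Day 95 Visits comparing active to placebo".
- Range of motion is analysed for five motions, passive and active, at four visits, on more than one scale: "MMRM will be performed to estimate absolute and percent change from baseline treatment effect compared to baseline of the contralateral shoulder at Day 22", with the later visits following in the same sentence (SAP 7.9.2.1; SAP 7.9.2.2 is parallel).
- Satisfaction is tested item by item: "A Wilcoxon rank sum nonparametric test will be used to compare EN3835 to placebo for all the individual questions of Subject Satisfaction" (SAP 7.9.2.8).
- Hand-behind-back, global severity, change in severity, investigator assessment and subject satisfaction each come with null and alternative hypotheses and a p value. The MMRM secondaries come with p values and 95% CIs.

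Several secondary objectives are worded as efficacy objectives, for example "To assess the efficacy of EN3835 for the treatment of AC of the shoulder using passive range of motion (PROM" (Protocol 3.1). Exploratory analyses have their own tier (SAP 7.9.3), so the secondaries do not inherit that label.

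**The concern.** A common significance level with no order and no label leaves the status of a secondary result undefined. Under the wording of SAP 6.1, any secondary p value below 0.05 can be called significant, including when the Day 95 primary test has failed. The SAP does make one analysis depend on the primary: the tipping-point analysis is dropped if the primary result is not significant (SAP 6.3.1 and 7.9.4.1). It places no such condition on the secondaries.

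At stake is the reading of the study report. With this many contrasts, a few p values below 0.05 are expected from a treatment that does nothing, and the plan gives a reader no agreed way to discount them.

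**Working it through.** **1. The plan's own figure.** The documents give no count of secondary tests and no family-wise rate. The figure that can be checked is the sample size, which shows where the 0.05 was allocated. Inputs (Protocol 9.1): "Given a mean change from baseline value of 38.6 for the EN3835 group and 27.6 for the placebo group with an SD of 21.6" and "a 1:1 randomization and a type I error of 0.05 with a power of 85" percent.

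- Difference: 38.6 − 27.6 = 11.0.
- Normal approximation: n per arm = 2 × (1.960 + 1.036)² × 21.6² / 11.0² = 69.2, so 70 per arm, 140 in total.
- t-test version: 70.2, so 71 per arm, 142 in total, with power 85.4%.
- Dropout: 142 / 0.80 = 177.5, so 178, against the stated 180.

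The stated 142 is reproduced. The sample size is justified for the Day 95 composite only.

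**2. Counting the secondary contrasts (SAP 7.9.1 and 7.9.2).**

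| Measure | Contrasts | At Day 95 |
|---|---|---|
| PROM: 5 motions × 4 visits × 2 scales (absolute, percent) | 40 | 10 |
| AROM: same | 40 | 10 |
| Hand behind back: 4 visits | 4 | 1 |
| ASES pain and function: 2 × 4 visits | 8 | 2 |
| ASES composite, Day 64 | 1 | 0 |
| Pain upon movement: 2 visits | 2 | 1 |
| Global severity: 4 visits | 4 | 1 |
| Change in severity: 4 visits | 4 | 1 |
| Investigator assessment: 2 visits | 2 | 1 |
| Subject satisfaction: 4 items × 2 visits | 8 | 4 |
| **Total** | **113** | **31** |

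The SAP prints 153. Forty are removed because, by the definitions in SAP 4.7.2, absolute change relative to the contralateral shoulder is Di − D1 = (ASi − CS1) − (AS1 − CS1) = ASi − AS1. That equals plain absolute change, and the models carry no baseline covariate that could separate the two.

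The total is not sensitive to borderline choices. It is 112 without the Day 64 composite. It is 115 if the composite were also tested at Days 22 and 43, which are secondary endpoints in Protocol 3.1 but only summarised in SAP 7.9.1.1.

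**3. Expected number of false positives.** With no true effect and each test at level 0.05:

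- All: 113 × 0.05 = 5.65.
- Day 95 only: 31 × 0.05 = 1.55.

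Expectations add whatever the correlation, so no assumption about correlation is needed. By symmetry about half would favour EN3835, roughly 2.8 and 0.8. This is approximate, because the four change-in-severity tests have no direction.

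**4. Chance of at least one.** This does need the correlation, which the documents do not give. *Assumption:* normal test statistics with one common correlation ρ, written z = √ρ·g + √(1−ρ)·e, with g and e independent standard normal variables and e drawn separately for each test. Then

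P(at least one) = 1 − E over g of { Φ[(1.96 − √ρ·g)/√(1−ρ)] − Φ[(−1.96 − √ρ·g)/√(1−ρ)] }^k

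For results favouring EN3835 only, the second Φ term is dropped (0.025 per test).

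| ρ | k = 113, either direction | k = 113, favouring EN3835 | k = 31, either direction |
|---|---|---|---|
| 0 | 0.997 | 0.94 | 0.80 |
| 0.3 | 0.96 | 0.60 | 0.67 |
| 0.5 | 0.80 | 0.42 | 0.51 |
| 0.7 | 0.52 | 0.26 | 0.34 |
| 0.9 | 0.23 | 0.11 | 0.17 |

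A single ρ is a simplification. A simulation with separate assumed correlations across visits, scales, motions and instruments gave 0.98, 0.91, 0.77 and 0.55 for 113 tests as those correlations were raised from low to very high. These lie inside the same range.

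**The case against.** The strongest case on the other side has four parts.

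*This is a phase 2 trial with one primary contrast, and the secondaries do not touch its type I error.* This stands. A reader might infer from 113 tests at 0.05 that the trial's error rate is inflated. The documents do not support that, because one Day 95 test is the primary endpoint and the secondary tests do not enter it. The Day 64 composite test sits in the primary-analysis section, but SAP 2 lists it as secondary and SAP 6.3.1 defines the primary endpoint at Day 95 only.

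*The tests overlap heavily.* This also stands in part. Percent change divides the same quantity by the baseline deficit, and passive and active range cover the same five motions. Overlap lowers the chance of at least one false positive. It leaves the expected number at 5.65 and makes the false positives arrive in clusters.

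*SAP 6.1 only fixes sidedness and level, and SAP 6.1 also calls for estimates and 95% CIs.* It is true that no passage defines trial success, an efficacy claim or a go/no-go rule from a secondary, so it would be too much to say that the plan will declare efficacy on one. But the rule permits each to be called significant and nothing limits what follows.

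*The earlier study shows the danger.* A reader might infer that a stray secondary result has driven this program before, since the sample size rests on a post hoc subgroup (Protocol 9.1). That was selection of a subgroup by MRI severity, with an effect on the pain and composite scores. This trial answers it by testing the composite prospectively as its primary. It is not a precedent for secondary multiplicity and should not be used as one.

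**Conclusion.** The gap is real and of moderate weight. SAP 6.1 and 7.9.1 to 7.9.2 together put 113 distinct secondary contrasts, 31 at Day 95, at two-sided 0.05 with no hierarchy, gate or nominal label. With no true effect, about 5.65 of them (1.55 at Day 95) would be called significant, about half in favour of EN3835. That figure assumes only that each test has its stated size.

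It is tempting to give a single family-wise rate such as 80%. That value holds only at a common correlation of 0.5, which the documents do not supply. The supportable statement is a range: 0.23 to 0.997 for ρ from 0.9 to 0, and 0.11 to 0.94 for results favouring EN3835. Nor can one say that at least one favourable false positive is the likely outcome: at ρ = 0.5 its chance is 0.42. The documents set no family-wise target for the secondaries, so these rates describe how the results would behave and do not breach a stated limit.

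The consequence is confined to the conclusions drawn from secondary results. The primary test stands as planned.

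**What to change.** Revise SAP 6.1 to state that:

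- the only confirmatory efficacy test is EN3835 versus placebo for change from baseline in the adapted ASES composite at Day 95, two-sided 0.05;
- all other efficacy p values, including the Day 64 composite and every test in 7.9.2, are nominal, are reported with estimates and 95% CIs where available, and will not be described as statistically significant.

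The cost is a few sentences and matching table footnotes, settled before unblinding. No data collection or analysis model changes, and every planned estimate, interval and p value is still reported. The downside for the sponsor is that an isolated secondary p value below 0.05 can no longer be presented as a significant finding.

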6.2. Derived Variables

Table 16 defines the derived variables for study parameters.

Variable	Definition	
Height (cm)	If height is recorded in inches, then height is equal to the recorded value multiplied by 2.54 and then rounded to 1 decimal place.	
Weight (kg)	If weight is recorded in pounds, then weight is equal to the recorded value multiplied by 0.454 and then rounded to 1 decimal place.	
Body Mass Index (BMI)	BMI will be computed using height and body weight measured at Screening as, BMI $(kg/m^2) =$ Weight $(kg) /$ Height $(m)^2$	
Relative Day 1	The day of first injection of study drug will be considered as relative Day 1.	
Study Day (for assessment on or after Day 1)	Study Day will be computed as, Date of Assessment – Date of Day 1 + 1	
Study Day (for assessment before Day 1)	Study Day will be computed as, Date of Assessment – Date of Day 1	
Baseline	Baseline is defined as the last non-missing measurement/assessment prior to the first dose of study drug.	
	The assessments made in unscheduled visits will be considered in calculation of baseline, if the unscheduled assessment is the closest value preceding the first dose of study drug.	
Baseline for Vital Signs on Injection Days	For vital signs on injection days, the baseline value will be the vital sign measure immediately prior to the first dose of study drug.	
Change from Baseline	Change from baseline will be derived as, post-baseline visit/time point value – the baseline value.	
Last Date in Study	Last date in study is defined as:	
	• The date of End of Study (EOS) Visit (Day 95) if the subject completes the study	
	• The date of early termination visit if the subject is terminated early from study at a non-scheduled visit	
	• The date of the latest scheduled visit if the subject is terminated early from study at a scheduled visit or lost to follow-up.	
Duration of AE	AE end date – AE start date + 1	
AE Onset Day (for AE onset date on or after date Day 1)	AE start date – Date of Day 1 + 1	
AE Onset Day (for AE onset date before date of Day 1)	AE start date – Date of Day 1	

Table 16:Derived Variables and Definition

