8.2.6. Vital Signs

Vital signs will be obtained after the subject has been seated for 5 minutes (minimum) and will include systolic and diastolic blood pressures, pulse rate, respiratory rate, and body temperature. The results, date, and time for all vital sign assessments will be recorded.

On days that study treatment is administered (the Day 1, 22, and 43 Visits), vital signs will be taken up to 4 hours prior to dosing and at 15 and 30 minutes after dosing (body temperature is not required at the 15-minute postdose time point). The subject's vital signs must be stable, or repeated until stable, before the subject can leave direct observation.

The investigator will review all vital sign values for clinical significance. Any change from the Screening Visit in vital signs that is considered by the investigator to be clinically significant will be recorded as an AE (or SAE, if appropriate).

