3.3. Study Treatment

Subjects will be given a dose of 0.58 mg of EN3835 or placebo per treatment session for up to 3 treatment sessions at least 21 days apart (the Day 1, 22, and 43 Visits).

The injection concentration for each treatment visit is outlined in Table 3 below.

Table 3:Study Treatment

Cohort	Route of Administration	Number of Injections at Each Treatment Visit	Dose at Each Treatment visit (mg)	Number of Treatment Visits	Total Dose Administered (mg)
EN3835	Pericapsular (periarticular) Injection	1	0.58	3	1.74
Placebo	Pericapsular (periarticular) Injection	1		3	

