4.8.2.2. Vital Signs

Vital signs will be analyzed for observed value and change from baseline separately for vital signs on injection days and vital signs at each visit (excluding post injection time points on injection days). Refer to Table 16 for the definition of baseline.

In addition, subjects reporting any sponsor-defined PCI vital sign values during the study will be analyzed.

Vital sign values are PCI if they meet both the observed value criteria and the change from baseline criteria. The PCI vital sign values are presented in Table 14 below.

Parameter	PCI Low	PCI High
Systolic blood pressure	≤90 mm Hg and decrease ≥20 mm Hg from baseline	≥140 mm Hg and increase ≥20 mm Hg from baseline
Diastolic blood pressure	≤60 mm Hg and decrease ≥15 mm Hg from baseline	≥100 mm Hg and increase ≥15 mm Hg from baseline
Pulse rate	≤50 bpm and decrease ≥15 bpm from baseline	\geq 125 bpm and increase \geq 15 bpm from baseline
Respiratory rate ≤ 12 brpm and decrease ≥ 7 brpm from baseline		≥25 brpm and increase ≥7 brpm from baseline
Temperature		≥38.3°C and increase ≥1.1°C from baseline

Table 14:Potentially Clinically Important Vital Sign Criteria

bpm=Beats per minute; brpm=Breaths per minute; PCI=Potentially clinically significant

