7.10.4. Vital Signs

Student *t* test (2-sample *t* test) will be used to compare EN3835 to placebo for change from baseline in the vital signs (SBP, DBP, pulse rate, respiratory rate, body temperature, and body weight) at Day 1, 22, 43, 64, and 95 Visits.

The null and alternative hypotheses for this test will be as below:

H₀: There is no significant difference in mean change in vital sign parameters between the 2 treatment groups.

Vs

H₁: There is a significant difference in mean change in vital sign parameters between the 2 treatment groups.

Vital signs (SBP, DBP, pulse rate, respiratory rate, body temperature) taken on the injection days will be summarized across the required measurement time points (15 minutes and 30 minutes post injection) for each treatment group using descriptive statistics for observed and change from baseline values.

Vital signs taken at each visit will be summarized across study visits not including the post injection time points for each treatment group and overall using descriptive statistics for observed and change from baseline values along with *p* value.

Proportion of subjects reporting with PCI vital sign values will be compared for EN3835 to the placebo treatment group using Fisher's exact test. Refer to Table 14 for PCI criteria.

The null and alternative hypotheses for this test will be as below:

 H_0 : p1 = p2 (Proportion of subjects having PCI vital sign values are equal in treatment groups)

Vs

 H_1 : $p1 \neq p2$ (Proportion of subjects having PCI vital sign values are unequal in treatment groups)

Where,

p1: Proportion of subjects having PCI vital sign values in EN3835 treatment group.

p2: Proportion of subjects having PCI vital sign values in placebo treatment group.

The PCI vital sign values will be summarized by treatment groups. In addition, the p value for treatment comparison will be presented.

A listing will be presented for vital signs results.

7.10.5. 12-Lead ECG

The investigator interpretation of ECG results (normal, abnormal not clinically significant, or abnormal clinically significant) will be summarized by each treatment group and overall using frequency counts and percentages.

A listing of investigator interpretation of ECG results will be presented.

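### Post-injection vital-sign changes at Days 22 and 43 are measured from the Day 1 pre-injection value, so they combine the acute change with 3 to 6 weeks of between-visit change

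*SAP*

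**What the plan says.** Injections are planned as "treatment sessions at least 21 days apart (the Day 1, 22, and 43 Visits"). On each of those days, Protocol Section 8.2.6 has readings before and after the injection: "vital signs will be taken up to 4 hours prior to dosing and at 15 and 30 minutes after dosing". SAP Section 3.16.5 repeats this.

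SAP Table 16 has three relevant rows:

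- General baseline: "Baseline is defined as the last non-missing measurement/assessment prior to the first dose of study drug".
- Injection-day vital signs: "For vital signs on injection days, the baseline value will be the vital sign measure immediately prior to the first dose of study drug".
- Change: "Change from baseline will be derived as, post-baseline visit/time point value" minus the baseline value.

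SAP Section 7.10.4 then plans two tables. In the injection-day table, vital signs "taken on the injection days will be summarized across the required measurement time points (15 minutes and 30 minutes post injection") are described as observed values and changes, with no p value mentioned. For the other table, "Vital signs taken at each visit will be summarized across study visits not including the post injection time points", and this is where the p value is attached. The same section lists two-sample t tests at Days 1, 22, 43, 64 and 95.

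For PCI values, Section 4.8.2.2 says: "Vital sign values are PCI if they meet both the observed value criteria and the change from baseline criteria". Subjects with any such value during the study are counted, and Section 7.10.4 compares the arms by Fisher's exact test. Nothing excludes post-injection readings from that count or gives it a different baseline. Neither document defines a same-day pre-to-post change for Days 22 and 43.

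**The concern.** Readings at 15 and 30 minutes are there to show what happens straight after an injection. Protocol Section 6.1 ties the 30-minute observation to immediate immunological events, and hypersensitivity is an adverse event of special interest. At the second and third injections, the natural reference is the reading taken earlier that day. Table 16 uses the Day 1 reading instead, so the derived change carries whatever else moved in the interval. That adds noise to the descriptive table. Because the PCI rule includes a change criterion, it can also move individual subjects into or out of a count that is formally tested. The separate injection-day row gives essentially the same reference as the general row, so it is unclear what it was meant to add.

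**Working it through.** There is no plan figure to reproduce, because the point concerns a definition. The checks are on timing, decomposition, classification and size.

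**1. Age of the reference.** Day 22 - Day 1 = 21 days; Day 43 - Day 1 = 42 days. With the +3 day windows in the Schedule of Activities, the ranges are 21-24 and 42-45 days, or roughly 3 and 6 weeks.

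**2. What the derived change contains.** For injection day k:

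post(k) - pre(1) = [post(k) - pre(k)] + [pre(k) - pre(1)]

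The first bracket is the acute change and the second is between-visit change. On Day 1 the second bracket is zero, so Day 1 post-injection changes are unaffected.

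**3. Effect on a PCI flag.** Table 14 defines PCI low for systolic pressure as 90 mmHg or below and a fall of at least 20 mmHg. Two hypothetical subjects:

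| Day 1 pre | Day 22 pre | Day 22 post | Change from Day 1 | Same-day change | Flag, Day 1 baseline | Flag, same-day |
|---|---|---|---|---|---|---|
| 105 | 120 | 88 | 88 - 105 = -17 | 88 - 120 = -32 | No | Yes |
| 115 | 100 | 90 | 90 - 115 = -25 | 90 - 100 = -10 | Yes | No |

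Errors can go either way.

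**4. Variance of the change.** The documents give no SDs, so these are assumptions. Let sw be the within-visit SD and sb the between-visit SD within a subject.

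- Day 1 baseline: SD = sqrt(2·sb² + 2·sw²). Same-day: SD = sqrt(2·sw²).
- With sw = 5 and sb = 6, 8, 10, 12 mmHg, the SDs are 11.0, 13.3, 15.8 and 18.4, against 7.1. The variance ratio (sb² + sw²)/sw² runs from 61/25 = 2.4 to 169/25 = 6.8.
- A second set of assumptions uses correlations: 0.8-0.9 between same-day readings and 0.5-0.7 between visits. The ratio (1 - r_between)/(1 - r_same) runs from 0.3/0.2 = 1.5 to 0.5/0.1 = 5.

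Taken together, the variance is about 1.5 to 7 times larger with the Day 1 baseline.

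**5. Full systolic PCI-low rule.** This was simulated with level and change applied together. The model is a subject mean, plus an independent visit deviation (SD 6-12), plus an independent reading deviation (SD 5). Mean systolic pressure of 120-130 and between-subject SD of 10-14 mmHg are further assumptions.

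| Per reading | Day 1 baseline | Same-day baseline |
|---|---|---|
| Flagged by noise alone, no acute effect | about 0.03-2.6% | under 0.04% |
| True 30 mmHg fall reaching 90 or below, not flagged | about 5-16% | about 3-6% |

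**6. The t tests in Section 7.10.4.** If the Day 1 test uses the by-visit table, the only Day 1 value there is the pre-injection reading. That reading is the baseline, so every change is zero. If it uses post-injection readings, it conflicts with the paragraph that attaches the p value to a table without them.

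**The case against.** A fixed pre-treatment reference is a common convention and is consistent with the rest of the plan: the general baseline is also before the first dose, and Protocol Section 8.2.6 judges clinical significance against the Screening Visit. Nor is the same-day change a pure acute effect. The pre-dose reading may be up to 4 hours old, and vital signs are specified seated while the subject should stay supine for 20 minutes after injection. Much is also recoverable: observed post-injection values and by-visit pre-injection values are both summarized, and all results are listed. These points stand as limits on severity. They do not supply a same-day change per subject, its spread, or a PCI flag based on it.

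Three stronger readings are tempting, and the documents do not support them.

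- *Acute reactions to repeat injections would be missed.* Subjects are directly observed for 30 minutes, vital signs must be stable before release, and the investigator reviews every value and reports clinically significant changes as adverse events. Events of special interest are defined by preferred term and compared between arms, and drug-related events are tabulated by treatment session. None of this uses the derived change.
- *Large error rates follow from the change criterion.* On the change part alone, with sw = 5 and sb = 6-12, noise falls of 20 mmHg or more have probability 1 - Φ(20/SD) = 3.5-13.8%, against 0.2%. True 30 mmHg falls read as under 20 with probability Φ(-10/SD) = 18-29%, against 8%. The PCI rule also requires a level, so these are not PCI error rates.
- *The Day 1 t test is certainly degenerate.* The sentence listing the t tests does not itself exclude post-injection readings. The text is inconsistent, and that is as far as it goes.

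**Conclusion.** The point holds as a defect in the safety derivation. At Days 22 and 43, the stated baseline does not isolate the acute post-injection change, and the PCI rule inherits this wherever it is applied to post-injection readings. Concurrent randomized placebo balances non-treatment drift in the arm means, so this is not a case for bias in the mean comparison from that source. What remains is added variance and modest misclassification of individual PCI values, of the size shown in steps 4 and 5. The wording and the decomposition are certain. The percentages depend on the assumed mean and SDs, and cover only the systolic PCI-low rule. Because the remedy is nearly free, the sponsor should make the change, but it does not threaten the trial's main safety conclusions.

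**What to change.** In SAP Table 16, define the reference for 15- and 30-minute vital signs as the last pre-injection value on the same injection day. State in Section 4.8.2.2 that the Table 14 change criterion uses this reference for post-injection readings. Keep the Day 1 baseline for the by-visit table.

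In Section 7.10.4, reconcile the t test listed for Day 1 with the by-visit table that leaves out post-injection readings, and attach the between-arm comparison to the 15- and 30-minute changes on each injection day.

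The cost is a few lines of SAP text and a small programming change. All the readings are already collected. The one drawback is that vital signs would then have two reference values, so every table and listing must label which one it uses.
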